7.1. Primary Endpoints

The primary endpoint of the study is to achieve non-inferiority of transvaginal repair with Xenform over native tissue repair at 36 months as compared to baseline.

Success will be based on a composite of objective and subjective measures, and subjects will be considered a surgical success if each of the three criteria is met:

1. Subjective success is achieved if the patient denies symptoms of vaginal bulging per PFDI-20 question 3, answering “no” or “yes” but “Not at all” bothersome (<2).
2. Anatomic success (in the operated compartment):
 - Anterior segment: Leading edge of anterior prolapse is at or above the hymen or POP-Q point Ba \leq 0.
 - Apical segment: The vaginal apex does not descend more than one-half into the vaginal canal (i.e. POP-Q point C < -1/2 TVL) for multi-compartment prolapse or POP-Q point C \leq 0 for single compartment apical prolapse.
3. No retreatment for POP: No additional surgical treatment for POP in the segment(s) of the vagina treated at the index surgery or no pessary use since index surgery (i.e., ‘treated segment’ refers to the target compartments in this study, which are the anterior and apical compartments).

Additionally, a co-primary endpoint of the study is to achieve non-inferiority of transvaginal repair with Xenform to native tissue repair for safety by comparing rates of serious device or serious procedure related complications between baseline and the 36 month time point. Serious injury is defined per 21 CFR 803.3, i.e., life threatening, results in permanent impairment of a body function or permanent damage to a body structure or injury or illness that requires medical or surgical intervention to preclude impairment of a body function or permanent damage to a body structure.

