10.2.1. Voluntary Withdrawal

Subjects may withdraw from the study at any time. At the time of withdrawal, the Investigator shall document the reason for the withdrawal. For subjects who withdraw from the study and decide to revoke their authorization to use and disclose their medical information, the information that has already been collected in the study record may continue to be used; however, no new information will be obtained or added.

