10.2.3. Lost to Follow-up

Before a subject may be considered lost to follow-up the Investigator must make the following attempts to contact the subject:

- Two documented telephone attempts
- One certified letter

If the subject is able to be reached and no longer wishes to participate in the study the Investigator shall document the reason for the withdrawal and complete End of Study Case Report Form. If the subject is not able to be reached after the required attempts to contact the subject are made and the subject has missed two consecutive follow-up visits within a 12 month calendar period, the subject may be considered lost to follow-up. The Investigator should document in the subject's medical record the attempts to contact the subject and reason for the withdrawal.

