10.2.5. Documentation of Early Termination

Once a subject withdraws from the study, the Case Report Form will be completed as appropriate up to the point of withdrawal and all Adverse Events shall be closed or documented as appropriate. Withdrawn subjects (who had the study procedure initiated) will be included in the Intent-to-Treat analysis and will not be replaced.

11. Study Methods

11.1. *Data Collection*

Study data will be collected per the schedule outlined in Table 11.1-1. All study data will be recorded on source documentation and captured within Case Report Forms for the purposes of this study. Study data will be monitored by Boston Scientific or representatives and as applicable on a regular basis as outlined in the study Monitoring Plan.

Table 11.1-1: Data Collection Schedule

Procedure/Assessment	Screening/ Enrollment Visit ²	Pre-Operative/ Baseline Visit	Surgery (≤3 mos from Baseline)	Discharge	Post-Operative Follow-up Visits ⁷					
					Month 2 Visit (± 4 Weeks)	Month 6 Visit (± 4 weeks)	Month 12 Visit (-4/+12 weeks)	Month 18 Visit (-4/+12 weeks)	Month 24 Visit (-4/+12 weeks)	Month 36* Visit (-4/+12 weeks)
Informed Consent	X									
Inclusion/Exclusion Criteria Review	X									
Demographics		X								
Urine Pregnancy Test	X	X								
Physical Examination		X								
Medical History ¹		X								
Pelvic Exam with vaginal length measurement		X			X	X	X	X	X	X
Assessment of Infection (vaginal, bladder)				X	X	X	X	X	X	X
Prolapse Grading (POP-Q Scoring)		X			X	X	X	X	X	X
PFDI-20 (Pelvic Floor Symptoms)		X			X	X	X	X	X	X
PFIQ-7 (Quality of Life)		X				X	X	X	X	X
PISQ-12 (Sexual Functioning)		X				X	X	X	X	X
PGI-I for Prolapse (Patient Improvement)						X	X	X	X	X
TOMUS Pain Scale		X			X	X	X	X	X	X
SSQ-8 for Surgical Satisfaction						X	X		X	X
EQ-5D for Health Status		X					X		X	X
Procedure and Assessments ³			X							
Post-Operative Assessment ⁴				X						
Assessment of Analgesic Intake		X			X	X	X	X	X	X
Assessment of Adverse Events ⁶			X	X	X	X	X	X	X	X
Assessment of Risk Factors ⁵		X			X	X	X	X	X	X
End of Study										X

*Primary Endpoint

¹Medical History at baseline includes documented absence of UTI or other vaginal infection (i.e. vaginal culture, etc.).

²The Screening/Enrollment Visit and Pre-Operative/Baseline Visit may be combined and occur up to 3 months prior to the study procedure with confirmed absence of infection.

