11.4.5. Follow-Up

Subjects will be scheduled for follow-up visits as outlined in Table 11.1-1 (Data Collection Schedule). The follow-up visit schedule begins from the day of the study surgery and includes visit windows (counted in calendar days).

Every effort should be made to do the follow-up visit within the window; however, if this is not possible, the site should attempt to complete the visit as soon as possible but before the next visit window opens. Follow-up visits will be considered missed once the visit window for the next follow-up visit opens. For the Month 36 visit, the visit is not considered missed until the last day of the visit window (i.e., +12 weeks).

Every effort should be made to conduct the follow-up visit at the study site location. However, if the subject cannot physically return to the site for any reason, the follow-up visit may be conducted at the subject's home with their consent and if allowed by local institutional policy and the IRB/EC. If a home visit is not possible, every effort should be made to conduct as much of the visit as possible by phone (i.e., assess adverse events, risk factors, and analgesic intake) and to send the subject questionnaires by mail for completion.

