12.1.1.2. Sample Size

The statistical power calculation is based on a non-inferiority assumption with a binary primary outcome. Objective success, based on a composite endpoint of anatomic and symptomatic success at 36 month is assumed to be 70.0%^{5-8, 16} for the native tissue arm. With type I error of 0.05 and type II error of 0.20 (power 80%), 362 subjects (181 subjects per arm) are needed to detect non-inferiority of transvaginal biologic to native tissue repair, using a margin of 12.0%.

To assess for safety, the overall complication rate (i.e., serious device-related or serious procedure-related adverse events) is anticipated to be approximately 14% per arm.⁹ With type I error of 0.05 and type II error of 0.10 (power 90%), 308 subjects (154 subjects per arm) are needed to detect non-inferiority with a margin of 11.6%.

To assess for office-based interventions for complications, the rate is anticipated to be approximately 2%.⁹ With type I error of 0.025 and type II error of 0.10 (power 90%), 330 subjects (165 subjects per arm) are needed to detect non-inferiority with a margin of 5%.

To assess for of surgical intervention for complications, the rate is anticipated to be approximately 1%.⁹ With type I error of 0.025 and type II error of 0.10 (power 90%), 260 subjects (130 subjects per arm) are needed to detect non-inferiority with a margin of 4%.

Non-surgical subjects will not be enrolled into this clinical study as all data on this cohort of subjects will be obtained from the AUGS Pelvic Floor Disorders Registry under Level 2 and analyzed with data from this clinical study.

Using the above calculations and assuming a 20% loss to follow-up rate, a total of 454 subjects (227 per study arm) will be enrolled to achieve the primary endpoint of success at 36 months.

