12.1.1.3. Statistical Methods

For the primary effectiveness endpoint, non-inferiority will be evaluated using a two-sided 90% confidence interval for the treatment difference (Xenform minus native tissue repair). If the entire confidence interval is above the margin (i.e., -12%), non-inferiority will be demonstrated. The confidence interval will be calculated based on the pooling of treatment differences across propensity score strata for a binary endpoint, as described in Section 12.2.3 (Propensity Score Methodology).

If any data on the primary efficacy endpoint is missing, multiple imputation will be performed in which the missing values will be imputed five times under a logistic distribution model, using a fully conditional specification that includes the treatment arm and the assessments of the treatment success endpoint at each of 2, 6, 12, 18, and 24 months. As

a sensitivity analysis, the comparison of treatments will also be performed using the following methods:

- Tipping point analysis
- Available cases only (i.e., only the subjects for whom the endpoint was assessed)

For the primary safety endpoint, the proportions will be calculated using for the numerator the number of subjects with an endpoint event and for the denominator the number of subjects in the analysis population (ITT and Per Protocol group). Non-inferiority will be evaluated using a two-sided 90% confidence interval for the treatment difference (Xenform minus native tissue repair). If the entire confidence interval is below the margin (i.e., 11.6%), non-inferiority will be demonstrated. The confidence interval will be calculated based on the pooling of treatment differences across propensity score strata for a binary endpoint, as described in Section 12.2.3 (Propensity Score Methodology).

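### The co-primary 36-month safety proportion counts women lost without a recorded serious event as event-free, and no sensitivity analysis is stated for incomplete safety follow-up

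*Combined protocol and SAP*

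**What the plan says.** - **Endpoint.** Section 7.1 defines the co-primary safety endpoint as "comparing rates of serious device or serious procedure related complications between baseline and the 36 month time point". The risk period is therefore the full 36 months.
- **Estimator.** Section 12.1.1.3 puts women with an endpoint event in the numerator and uses "for the denominator the number of subjects in the analysis population (ITT and Per Protocol group") for the denominator. Non-inferiority is declared if the two-sided 90% interval lies below 11.6%. Section 12.2.3 builds that interval from simple proportions within propensity strata, with no censoring.
- **Who stays in.** Section 10.2.5: "Withdrawn subjects (who had the study procedure initiated) will be included in the Intent-to-Treat analysis and will not be replaced". The Per Protocol definition in Section 12.2.1 requires the assigned treatment and no major protocol deviation. It does not name incomplete follow-up as an exclusion.
- **When information stops.** After authorization is revoked, Section 10.2.1 keeps data already collected; "however, no new information will be obtained or added". Section 10.2.3 has two conditions for loss to follow-up: "If the subject is not able to be reached after the required attempts to contact the subject are made", and two consecutive visits missed within 12 months.
- **Expected loss.** Section 12.1.1.2 reaches 227 per arm "assuming a 20% loss to follow-up rate".
- **Missing data.** Section 12.1.1.3: "If any data on the primary efficacy endpoint is missing, multiple imputation will be performed", followed by tipping-point and available-case analyses for the same endpoint. The 12-month interim text (12.3.8.2) likewise imputes only the efficacy composite. The safety paragraph has no counterpart.

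**The concern.** A woman who leaves at month 8 with no serious event on record has unknown status for the remaining 28 months, yet she enters the co-primary test as a known non-event. Events recorded before she left do count.

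In a non-inferiority test this matters in one particular situation. If Xenform truly has more serious complications and both arms lose women at similar rates, both observed rates fall by the same proportion. The higher rate then falls by more points and the difference moves toward zero. The margin does not move with it, so the chance of wrongly declaring safety non-inferiority exceeds the planned 5%.

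Other planned analyses touch event timing: interval event rates in 12.1.2.3, and Cox models in 12.3.4 and 12.3.5.2 for other adverse-event questions. None of them shows how far the co-primary conclusion depends on women with unknown safety status.

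**Working it through.** **1. The plan's own figures.** Inputs from 12.1.1.2: 14% per arm, margin 11.6%, type I error 0.05, power 90%.

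n = 2 × 0.14 × 0.86 × (1.645 + 1.282)² / 0.116² = 153.3, so 154 per arm, as stated. The effectiveness size also reproduces: 2 × 0.70 × 0.30 × (1.645 + 0.842)² / 0.12² = 180.3, so 181, and 181 / 0.80 = 226.25, so 227. At 14% in both arms, safety power is 90.1% with 154 per arm and 97.2% with 227. The issue is bias, not sample size.

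**2. Effect of the counting rule.** Let p be the true 36-month rate, e the share of events that are perioperative (before any loss), and L the share of women without complete safety follow-up, with loss spread evenly over 36 months. On average a lost woman misses half of the later risk, so

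observed rate = p × [e + (1 − e)(1 − L/2)].

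With d the observed difference and SE the unpooled binomial standard error at 227 per arm,

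one-sided error = Φ((0.116 − d)/SE − 1.645).

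The true rates are set at the margin: 25.6% Xenform (14% + 11.6%) and 14% control. The documents give neither e nor L by arm for safety, so both are varied.

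Worked case, e = 0 and L = 0.20 in both arms: the observed rates are 23.04% and 12.60%, d = 10.44 points and SE = 3.56 points. The error is Φ(1.16/3.56 − 1.645) = 9.4%.

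| Without complete safety follow-up (Xenform / control) | e = 0.9 | e = 0.8 | e = 0.5 | e = 0 |
|---|---|---|---|---|
| 0 / 0 | 5.0% | 5.0% | 5.0% | 5.0% |
| 5% / 5% | 5.1% | 5.2% | 5.4% | 5.9% |
| 10% / 10% | 5.2% | 5.3% | 5.9% | 6.9% |
| 20% / 20% | 5.3% | 5.7% | 6.9% | 9.4% |
| 25% / 15% | 5.6% | 6.3% | 8.9% | 14.9% |
| 10% / 30% | 4.8% | 4.6% | 3.9% | 3.0% |

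If the true rates are equal and loss is equal, both observed rates fall alike and the difference is unbiased.

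**3. Check with five strata.** A simulation used the n_j/n weights of 12.2.3, 12,000 trials per scenario, non-informative loss of 20% in both arms, and three patterns of Xenform share across strata. The stated proportion gave 9.2-10.0% (e = 0), 7.3-7.5% (e = 0.5) and 5.5-5.9% (e = 0.9). A stratified Kaplan-Meier estimate gave 5.4-5.5%, 5.4-5.8% and 5.3-5.6%.

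**4. Could a passing result be reversed?** These are hypothetical, unstratified counts. 36 vs 25 of 227 gives a difference of 4.85 points, SE 3.19 and an upper 90% limit of 10.1%, which passes. With even accrual and 20% loss about a tenth of events are missed: 36/0.9 = 40 and 25/0.9 = 27.8, that is, about 4 and 3 missed. At 40 vs 28 the upper limit is 10.8%, still a pass. Reversal needs, for example, 44 vs 30 (upper limit 11.9%): 8 missed Xenform events, twice the expected number. That would require informative loss.

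**The case against.** **Timing.** Even accrual is the least supported assumption. Every related category in Table 21.4-1 requires a timely relationship to the procedure, and controls can qualify only through the procedure, because Section 21.3 assesses device-relatedness in the Xenform cohort only. This stands as a reason not to lead with 9.4% or 14.9%. It also cuts the other way: late device-related events could fall in the Xenform arm alone, which would enlarge the bias. That pattern was not modelled.

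**Amount of loss.** A reader might infer that 20% of women will have no safety data. The documents do not support that. The 20% sizes the effectiveness endpoint, which needs a POP-Q examination. Section 11.4.5 lets sites "conduct as much of the visit as possible by phone (i.e., assess adverse events, risk factors, and analgesic intake"), and Table 21.6-1 requires serious related events to be reported through the end of the study. This stands, so 20% is probably at the upper end for safety. But phone contact is data collection and not an analysis rule, and it does not reach women who cannot be contacted.

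**Direction.** A reader might infer that the rule always favours Xenform. It does not: heavier control loss makes the test conservative.

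**Replacing the estimator.** A reader might conclude that the primary safety estimate must change. Events over the full analysis set is an explicit, pre-specified rule. Enrollment closed in December 2016 (Table 10.1-1), and 12.3.8 plans a comparative 12-month safety test. Changing the primary estimator around that point carries its own risk of bias, and Kaplan-Meier gains only about 0.3 points or less when 90% of events are perioperative. This objection stands and limits the fix to added analyses.

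**Scope.** The Synopsis refers to a Statistical Analysis Plan that may hold more than the supplied text. The point is confined to that text.

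**Conclusion.** The point holds. The rule in 12.1.1.3 treats unknown safety status as no event, and the supplied text states no analysis that would show the consequence for a co-primary test.

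The size is modest if few women lack safety contact or most serious events are perioperative: 5.1-5.3% against 5% with 5-10% incomplete and 80-90% perioperative. It reaches 6.9-9.4% at 20% loss in both arms with half or fewer of the events perioperative, and it can be larger if Xenform loses more women. These figures assume true rates at the margin, loss spread evenly over 36 months and unrelated to risk, and the same event timing in both arms. Non-informative loss of the expected size would not overturn the example in the working. The reason to act is that nobody reading the planned output could tell whether the actual loss was benign.

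This should be fixed. Confidence is medium: the omission is clear in the text, while its effect depends on timing and loss that the documents do not report.

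**What to change.** Keep the stated proportion as the primary safety estimate. Add to 12.1.1.3, before the 36-month analysis:

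1. **A censoring-aware sensitivity analysis.** Estimate the 36-month cumulative incidence of a first serious device- or procedure-related complication by arm within each propensity stratum. Use Kaplan-Meier with Greenwood variance, or Aalen-Johansen with its own variance if unrelated death is treated as competing. Censor at the last contact with adverse event assessment, and count a completed Month 36 visit as full follow-up. Combine the stratum differences and variances with the n_j/n weights of 12.2.3.
2. **A tipping-point analysis for safety.** Extend the one already planned for effectiveness, varying by arm the event probability of women without complete safety follow-up. Item 1 alone does not cover informative loss.
3. **The number of such women by arm.**

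State that the safety non-inferiority conclusion is to be interpreted with these results.

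**Cost.** This needs plan wording, whatever approvals Section 14 requires, and programming. Onset dates are on the adverse event form (Table 21.6-1). The date of last contact with adverse event assessment must be confirmed as available, including for controls shared from the registry. At 20% loss the interval in item 1 is wider by about 10% with even accrual (mean SE 4.05 vs 3.67 points), 5% if half of events are perioperative (3.95 vs 3.75) and 1% if 90% are (3.85 vs 3.81). The power of the primary test is unchanged.

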12.1.2. Secondary Endpoints

Secondary endpoints will be to evaluate Xenform-related complications and subject reported outcomes as safety endpoints between baseline and 36 months:

1. Incidence of Xenform erosion
2. Incidence of Xenform exposure
3. Incidence of de novo dyspareunia
4. Improvement in subject specific outcomes at 36 months compared to Baseline (pelvic floor symptoms (PFDI-20), QOL (PFIQ-7), sexual functioning (PISQ-12), TOMUS pain scale)
5. Assessment of subject's level of improvement, measured by the Patient Global Impression of Improvement for Prolapse (PGI-I for Prolapse)
6. Absence of re-intervention or re-surgery for recurrence or persistence of POP or Xenform exposure/erosion
7. Surgical success based on the following composite outcome:
 - a. Subjective success: patient denies symptoms of vaginal bulging per PFDI-20 question 3, answering "no" or "yes" but "Not at all" bothersome (<2)
 - b. Anatomic success (in the operated compartment):
 - Anterior Segment: No anterior prolapse at or beyond the hymen or POP-Q point Ba<0
 - Apical Segment: The vaginal apex does not descend more than one-half into the vaginal canal (i.e. POP-Q point C < 1/2 TVL) for multi-compartment prolapse or POP-Q point C < 0 for single compartment apical prolapse.
 - c. No retreatment for POP (treated segment): No additional surgical treatment for POP in the segment(s) of the vagina treated at the index surgery or no

nessary use since index surgery ('treated segment' refers to the target compartments in this study, which are the anterior and apical compartments)

8. Device or procedure related incidence of the following: pelvic pain, infection, vaginal shortening, atypical vaginal discharge, neuromuscular problems, vaginal scarring, de novo vaginal bleeding, fistula formation and/or de novo voiding dysfunction

Definitions for the above listed adverse events are included in Section 21.2 (Definitions and Classifications). Rates of incidence for the adverse events will be stratified by primary or recurrent prolapse in both treatment groups.

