11.4.2. Pre-Operative/Baseline Visit

The Pre-operative/Baseline Visit will occur prior to the subject having surgery. The assessments below must be completed prior to study surgery. This visit may be combined

with the Screening/Enrollment Visit and occur up to 3 months prior to surgery with confirmed absence of infection.

- Urine pregnancy test
- Medical history and physical examination: assessment of urinary tract infection (UTI) or other vaginal infection
- Pelvic examination, vaginal length measurement
- Prolapse grading (POP-Q scoring)
- Assess baseline quality of life (PFIQ-7), sexual functioning (PISQ-12), pelvic floor symptoms (PFDI-20)
- Assess baseline level of pain (TOMUS pain scale) and analgesic use
- EQ-5D for health status
- Assessment of risk factors (includes menopausal status, estrogen use, age, smoking, diabetes status, body mass index, hysterectomy status, concomitant procedures, surgeon training and expertise)

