11.4.6. Month 2 Visit (± 4 Weeks)

- Pelvic exam with vaginal length measurement
- Assessment of infection (vaginal, bladder)
- Prolapse grading (POP-Q Scoring)
- Assess pelvic floor symptoms (PFDI-20)
- Assessment of pain (TOMUS pain scale) and analgesic intake
- Assessment of adverse events (device, procedure, and pelvic floor related)
- Assessment of risk factors

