12.1.2.1. Hypotheses

Statistical testing will be performed to determine if the de novo dyspareunia rate of treatment group is non-inferior to the control group. The null hypothesis is that the de novo dyspareunia rate in treatment group is greater than or equal to the rate in control group plus margin:

$$H_0: \pi_{treatment} - \pi_{control} \geq \Delta$$

The alternative hypothesis is:

$$H_a: \pi_{treatment} - \pi_{control} < \Delta$$

where $\pi_{treatment}$ and $\pi_{control}$ are the de novo dyspareunia rate in treatment group and control group respectively, and $\Delta > 0$ is defined as the non-inferiority margin.

Statistical testing will be performed to determine if the AE incidences (pelvic pain, infection, vaginal shortening, atypical vaginal discharge, neuromuscular problems, vaginal scarring, de novo vaginal bleeding, fistula formation and/or de novo voiding dysfunction) rate of treatment group is non-inferior to the control group. The null hypothesis is that the AE incidences rate in treatment group is greater than or equal to the rate in control group plus margin:

$$H_0: \pi_{treatment} - \pi_{control} \geq \Delta$$

The alternative hypothesis is:

$$H_a: \pi_{treatment} - \pi_{control} < \Delta$$

where $\pi_{treatment}$ and $\pi_{control}$ are the AE incidence rates in treatment group and control group respectively, and $\Delta > 0$ is defined as the non-inferiority margin.

The propensity score adjusted confidence intervals described in Section 12.2.3 (Propensity Score Methodology) will be used to summarize the mean score improvement of Quality of Life (PFIQ, PFDI, PISQ, TOMUS pain scale) of the Xenform (treatment) group compared to that of the native tissue repair (control) group.

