12.1.2.2. Sample Size

The rate of de novo dyspareunia is anticipated to be approximately 9%.¹⁷ With type I error of 0.05 and type II error of 0.20 (power 80%), 326 subjects (163 subjects per arm) are needed to detect non-inferiority with a margin of 7.9%.

The rate of AE incidence (pelvic pain, infection, vaginal shortening, atypical vaginal discharge, neuromuscular problems, vaginal scarring, de novo vaginal bleeding, fistula formation and/or de novo voiding dysfunction) is anticipated to be approximately 12%.¹⁵⁻¹⁸ With type I error of 0.05 and type II error of 0.20 (power 80%), 330 subjects (165 subjects per arm) are needed to detect non-inferiority with a margin of 8.9%.

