19.1. General

The risks and benefits of performing a transvaginal procedure to treat pelvic organ prolapse in the following subjects should be carefully considered due to additional risks associated with their conditions:

- Women planning future pregnancies
- Overweight women (weight parameters to be determined by the physician)
- Subjects with blood coagulation disorder
- Subjects with a compromised immune system or any other condition that would compromise healing
- Subjects with renal insufficiency or upper urinary tract obstruction

19.2. *Anticipated Adverse Events*

The following anticipated adverse events (AE) have been reported due to transvaginal prolapse repair, which includes repairs with the treatment device, but are not limited to:

- Abscess
- Adhesion
- Allergic, Hypersensitivity or Other Immune Reaction
- Bleeding (including vaginal or perineal)
- Bruising/Hematoma
- Dehiscence of vaginal incision
- Detrusor Instability
- De Novo Dyspareunia
- Edema/Erythema
- Exposure or Extrusion (Rejection)
- Erosion
- Fistula
- Foreign Body Reaction
- Granulation Tissue Formation
- Hemorrhage
- Incontinence (including fecal)
- Infection
- Inflammation (acute or chronic)
- Irritation
- Necrosis
- Neuromuscular Events (including groin and leg pain)
- Organ perforation
- Overactive bladder
- Pain
- Recurrence
- Resurgery
- Urinary Retention
- Urinary Tract Obstruction

- Vessel/Nerve Injury
- Vaginal Discharge (e.g. atypical)
- Vaginal Shortening or Stenosis
- Sexual Dysfunction

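### Vaginal length is measured at seven visits, but no listed analysis compares its change between arms, so shortening is assessed as a harm only through investigator-attributed adverse events

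*Combined protocol and SAP*

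**What the plan says.** **Measurement.** Section 11.4.2 requires "Pelvic examination, vaginal length measurement" before surgery. Section 11.4.6 lists "Pelvic exam with vaginal length measurement" at Month 2, and Section 11.4.7 repeats the item for Months 6, 12, 18, 24 and 36. Table 11.1-1 agrees.

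**Use in criteria.** For multi-compartment prolapse, Section 7.1 defines apical success as "The vaginal apex does not descend more than one-half into the vaginal canal", expressed as C < -1/2 TVL. TVL also enters inclusion criterion 3 (Section 9.2) and secondary endpoint 7. Section 7.1 does not say which visit's TVL applies.

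**Shortening as a harm.** Section 19.2 lists "Vaginal Shortening or Stenosis" among the anticipated events. Secondary endpoint 8 in Section 12.1.2 covers "Device or procedure related incidence of the following: pelvic pain, infection, vaginal shortening" and six other event types. These nine are tested together in Section 12.1.2.1: "The null hypothesis is that the AE incidences rate in treatment group is greater than or equal to the rate in control group plus margin". Section 12.1.2.3 adds rates of device- or procedure-related events over time and a between-group comparison. Section 12.3.4 adds a within-group Cox model that names shortening.

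**Ascertainment.** The investigator judges relatedness to the device (Section 21.3, Xenform cohort only) and to the procedure (Section 21.4). Section 10.1 assigns each physician to one arm. Section 12.1.2 refers to Section 21.2 for event definitions, but Table 21.2-1 defines only adverse event, serious adverse event and device deficiency. Section 21.1 places the event definitions in the Manual of Operations.

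**The concern.** Pain, quality of life and analgesic use each have a stated change-from-baseline analysis in Section 12.1.2.3, and EQ-5D has one in Section 12.3.6. Measured vaginal length has none. The plan therefore assesses a named harm through a yes/no event that must first be reported and then be judged related by someone who is not described as blinded and who treats in one arm only. Differences between physicians in reporting are thus nested within arm. The measured change has a baseline and depends far less on willingness to file an event.

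There is also a link to the primary composite. If the apical cut-off uses TVL from the same visit, a shorter vagina with C unchanged meets the criterion more easily. The existing use of TVL therefore cannot reveal shortening and could hide it.

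**Working it through.** **1. The plan's own figure.** Sections 12.1.2.2 and 12.1.2.1 give the nine-event test: rate 12% in both arms, margin 8.9 points, type I error 0.05 (taken as one-sided), power 80%.

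n per arm = (1.645 + 0.842)² × 2 × 0.12 × 0.88 / 0.089² = 165, as stated. The evaluable number at 36 months is 181 per arm (Section 8.1), and 181 / 0.80 rounds up to the 227 enrolled.

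**2. What that test says about shortening.** Suppose Xenform raises the nine-event rate only through shortening, by e points. With 181 per arm,

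P(non-inferiority declared) = Φ[(0.089 − e)/SE − 1.645], SE = √{[(0.12 + e)(0.88 − e) + 0.12 × 0.88]/181}.

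| e (points) | 0 | 2 | 3 | 5 | 8 |
|---|---|---|---|---|---|
| Probability | 83% | 62% | 50% | 28% | 8% |

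These excesses lie inside the margin, so a pass is not an error of the test. The test is simply not informative about shortening on its own.

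**3. Precision of the measured change.** The documents give no SD of change; 1 to 2 cm is assumed. Ignoring stratification, half-width of the 90% interval = 1.645 × SD × √(2/181):

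- SD 1.0 cm: 0.17 cm
- SD 1.5 cm: 0.26 cm
- SD 2.0 cm: 0.35 cm

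Imbalance between arms within propensity strata would tend to widen these.

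**4. The same difference seen both ways.** Assumptions: normal changes, mean control loss 0, an event defined as a loss above 2 cm, 181 per arm, two-sided 0.05. For a true mean difference of 0.5 cm and SD 1.5 cm, event rates are 1 − Φ(2/1.5) = 9.1% and 1 − Φ(1.5/1.5) = 15.9%.

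| Power for 0.5 cm | SD 1.0 | SD 1.5 | SD 2.0 |
|---|---|---|---|
| Mean change | 99.7% | 89% | 66% |
| Event, all captured | 53% | 49% | 37% |
| Event, half reported and attributed | 29% | 26% | 19% |

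For differences of 0.75 to 1.0 cm, event power over the same SDs is 71% to nearly 100% with full capture, and 38% to 88% with half captured.

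**5. The apical cut-off.** Take C = -4.5. At TVL 10 cm the cut-off is -10/2 = -5, and C fails. At TVL 8.5 cm it is -8.5/2 = -4.25, and the same C passes.

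**The case against.** The plan is less bare than a quick reading suggests.

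- **Length is used.** A reader might infer that the measurement is never used. It sets the TVL-based criteria in eligibility, the primary composite and endpoint 7. Nor do the documents say that length is collected because shortening is a harm; they give no reason.
- **Reporting is not confined to one composite.** Section 12.1.2.3 lists event rates separately from the overall rate, so shortening may well be tabulated on its own.
- **Generic summaries are promised.** The Synopsis promises summary tables and listings, and Section 12.3 specifies mean, SD and range for continuous variables. It would be too strong to say that nobody could see a difference. The Synopsis also defers to a Statistical Analysis Plan; the only analysis text available here is Section 12.
- **The attribution filter is loose.** Possible relatedness counts as related to the device, and a timely relationship is enough for a possible link to the procedure. Section 21.1 tells sites to submit unclear events.
- **The unseen dictionary may define shortening by measured length.** The documents do not settle this.
- **Measurement is partly protected, but not blinded.** Section 8 prefers a healthcare provider for follow-up POP-Q, with the treating surgeon as fallback.
- **The descent wording can be read as meaning the canal at that visit.** Same-visit TVL may be intended. The cut-off example also holds C fixed.

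All of this limits the strength of the point. None of it supplies a planned between-arm comparison of change in length.

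**Conclusion.** The gap is real and moderate in weight. No listed analysis compares change in vaginal length between arms, and shortening as a harm rests on investigator-attributed events whose definition cannot be checked in the document.

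A reader might infer that an arm difference would largely be missed. The documents do not support that: the answer depends on an SD, an event definition and a capture rate that they do not give, and the illustrative power ranges from very low to nearly complete. The supportable statement is that a small or moderate difference could be missed, while a large and well-captured one probably would not be. Nothing in the documents makes 0.5 cm an important difference; it is used only to show the contrast.

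No primary or co-primary conclusion is shown to change. The link to the primary composite is conditional on same-visit TVL being used. The point also treats the length taken at the pelvic exam and the TVL in the criteria as the same quantity, which the protocol does not state outright.

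**What to change.** 1. Add to Section 12.1.2.3: *Change in total vaginal length from baseline to Month 36 will be compared between arms using the continuous-outcome, propensity-stratified confidence interval of Section 12.2.3. Change to Months 2, 6, 12, 18 and 24 will be summarised descriptively by arm, with the number of women measured at each visit.* A plain change score fits the existing formula, which has no covariate term, so none should be added.
2. State which visit's TVL sets the C < -1/2 TVL cut-off. If it is the same-visit value, add a sensitivity analysis of the primary composite with the cut-off computed from baseline TVL.

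The cost is analysis-plan wording, one table and one sensitivity run on data already scheduled for collection. The downside is one more secondary comparison to interpret. Visits done by phone under Section 11.4.5 will have no length value. Where controls are shared from the registry, the sponsor should confirm that length was recorded at the same visits, because the protocol does not say so.
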